8.3 Analysis Populations

The primary efficacy population will be the Intent-to-Treat (ITT) and will include all randomized subjects who were dispensed study drug. Subjects will be analyzed within the treatment group to which they are randomized.

The primary safety population will be all treated subjects with at least one post-baseline assessment. For safety analyses, subjects will be classified based upon the treatment received.

The Per Protocol (PP) population will include all subjects in the safety population who complete the Week 10 evaluations without any significant protocol violations (i.e., any subject or investigator activity that could have possibly interfered with the therapeutic administration of the treatment or the precise evaluation of treatment efficacy). Analyses performed on the Per Protocol population will be considered supportive. The PP population will include subjects in the safety population who do not meet any of the following criteria:

- Violated the inclusion/exclusion criteria;
- Receives a strong CYP3A4 inhibitor (See [Appendix B](#));
- Receives an excluded medication for treatment of pruritus or PN;
- Have not been compliant with the dosing regimen (i.e. subjects must comply with 80–120% of the expected dosage of study medication during participation in the study);
- Out of visit window at the Week 10 visit by ± 7 days

Subjects that discontinue from the study drug due to an adverse event related to study treatment or documented lack of treatment effect will be included in the PP population. Prior to breaking the blind, other additional criteria may be added to the list to accommodate for unforeseen events that occurred during the conduct of the trial that result in noteworthy study protocol violations.

8.4 Subject Disposition

An accounting of all randomized subjects by disposition will be presented. Subjects who discontinue study drug prematurely or withdraw from the study will be summarized and listed, with a description of the reason for early termination/withdrawal.

8.5 Subject Characteristics

Demographic and other baseline characteristics will be summarized.

8.6 Prior and Concomitant Medications

Prior and concomitant medications will be coded by the World Health Organization Drug Dictionary to Anatomical Therapeutic Classification (ATC) and preferred drug name.

Prior therapies (including over-the-counter medications) used to treat the signs and symptoms of PN within the prior 2 years will be reported. Prior medications will be summarized by ATC level and preferred drug name and listed.

Concomitant medications will be summarized by ATC level and preferred drug name and listed. Concomitant medication use will be quantified and analyzed.

8.7 Treatment Compliance and Extent of Exposure

Compliance with study drug dosing will be determined based on tablet counts recorded on the eCRF. Compliance will be calculated by analyzing expected number of tablets returned versus actual number of tablets returned. Summaries of treatment exposure will also be produced.

8.8 Efficacy Analyses

All efficacy endpoints will be summarized within the ITT and PP populations using descriptive statistics by time point and treatment. Results including averaged imputed values will be summarized at Baseline, Week 2 (if available), 4, 10 and Follow-up, and the change from baseline for these measures will be summarized at Week 2, 4, 10 and Follow-up. The WI-NRS and change from baseline will also be presented for each study day.

8.8.1 Primary Efficacy

The difference in the primary efficacy outcome measure (WI-NRS 4-point responder rate at Week 10) will be tested using a CMH test controlling for the 'as randomized' stratification factors. Conceptually the hypotheses being tested are:

$$H_0: P_{Placebo} \geq P_{Serlopitant} \quad H_a: P_{Placebo} < P_{Serlopitant}$$

where $P_{Placebo}$ is the percent of placebo responders and $P_{Serlopitant}$ is the similar percent for serlopitant. The primary endpoint will utilize the missing data rules as outlined in [Section 8.2](#).

8.8.2 *Key Secondary Efficacy*

The differences between treatment groups for the key secondary efficacy endpoints, Week 2 WI-NRS 4-point responder rate and Week 4 WI-NRS 4-point responder rate, will be the CMH test identical to the one used for the primary endpoint.

The preceding tests are to be conducted for the ITT population and the PP populations.

8.8.3 *Additional Secondary Efficacy*

Additional secondary efficacy endpoints which may be drawn from the primary and key secondary imputations (including all WI-NRS endpoints) will be analyzed using the imputed data. Additional secondary efficacy endpoints otherwise will be analyzed using available data. P-values will be included for descriptive purposes only.

Additional secondary efficacy endpoints which are dichotomous (responder) will include analyses analogous to the primary and key secondary efficacy analyses.

Additional secondary efficacy endpoints based on change from baseline will be analyzed using an analysis of covariance (ANCOVA) model with treatment group and stratification factor as fixed effects and the baseline value as a covariate. Both least squares means and observed means will be presented.

To confirm the assumptions for the ANCOVA model (i.e., that the errors are normally distributed with equal variances), residuals will be examined using the Shapiro-Wilk test. If there is overwhelmingly strong evidence that the assumptions are not satisfied, the data will be rank-transformed prior to submitting to the ANCOVA. Results of the rank-transformed analysis then will be considered the primary analysis; however, results of the non-rank-transformed analysis will also be presented.

8.9 **Sensitivity Analyses**

8.9.1 *Last Observation Carried Forward*

In the first set of sensitivity analysis, missing values will be imputed using LOCF. Data will be imputed using LOCF unless the subject withdrew from the study due to a lack of efficacy, or the subject used an excluded therapy to treat worsening of pruritus or PN, in which case their responder status will be defined as non-responder. Each primary and key secondary endpoint will be analyzed as it was using the multiply imputed data.

8.9.2 *Repeated Measures Analysis*

The second set of sensitivity analyses will be performed on observed data.

The dichotomized primary and key secondary WI-NRS endpoints will be analyzed with a repeated measures logistic regression model (generalized estimating equations), with the dichotomized endpoint as the dependent variable and treatment, stratification factor and visit (Weeks 2, 4, 10) as independent factors

Change from baseline in DLQI to Week 10 will be analyzed with a repeated measures ANCOVA, with treatment, stratification factor and applicable timepoints as independent factors and a covariate of baseline value.

8.9.3 *Tipping Point Analysis*

A sensitivity analysis for the handling of missing data for the primary efficacy endpoint will be carried out using a tipping point analysis.

8.10 Safety Analyses

8.10.1 *Adverse Events*

The incidence of all AEs and treatment-related AEs will be tabulated by treatment received. These AEs will be classified by system organ class and preferred term using the Medical Dictionary for Regulatory Activities (MedDRA). For incidence reporting, if a subject reported more than one AE that was coded to the same system organ class or preferred term, the subject will be counted only once for that specific system organ class or preferred term. An overview of AEs, which includes subject incidence of AEs, treatment-related AEs, AEs by severity, SAEs, deaths, and AEs leading to discontinuation, will be presented.

SAEs will be listed and summarized in a similar manner to AEs.

8.10.2 *Clinical Safety Laboratory Results*

Clinical safety laboratory values will be measured by a central laboratory. Summary statistics for actual values and for changes from baseline will be tabulated for laboratory results by scheduled visit.

Subjects with clinical laboratory values outside of the normal reference range at any post-baseline assessment will be summarized. Shifts from baseline laboratory values will be tabulated.

8.10.3 *Vital Signs*

The observed data and change from baseline for each measurement day will be summarized with descriptive statistics.

8.10.4 *Electrocardiograms*

The overall ECG assessment (abnormal or normal) will be summarized and descriptively characterized, along with a summary of how many subjects developed a post treatment abnormal result.

8.10.5 *Physical Exams*

Physical exam finds will be recorded by the sites within medical history or adverse events and otherwise not summarized.

8.10.6 *Menstrual Diaries*

Menstrual diary dates will be used to summarize number and duration of menses.

8.10.7 *Hospital Anxiety and Depression Scale*

The observed data and change from baseline for the HADS will be summarized with descriptive statistics by scheduled visit. Both the Depression and the Anxiety subscales will be reported.

8.10.8 *Epworth Sleepiness Scale*

The observed data and change from baseline for the ESS will be summarized with descriptive statistics by scheduled visit.

8.10.9 *Potential for Physical Dependence*

In order to assess physical dependence and withdrawal, data collected during a 5-week post-drug observation period will be summarized. For each assessment, an on-drug baseline value is defined as Week 10 (for subjects completing treatment) or the last observation prior to last dose of study drug (for subjects that discontinued treatment early).

The observed data and change from on-drug baseline for the HADS will be summarized with descriptive statistics by time point (Day 3, Day 7, Weeks 2, 3, 4 and 5 post last dose of study drug). Both the Depression and the Anxiety subscales will be reported.

The observed data and change from on-drug baseline for the ESS will be summarized with descriptive statistics by time point (Day 3, Day 7, Weeks 2, 3, 4 and 5 post last dose of study drug).

Vital signs including change from on-drug baseline will be summarized with descriptive statistics for each post-study drug observation visit.

Overall ECG assessments (abnormal or normal), as well as observed and change from on-drug baseline for ECG parameters, will be summarized for the 5-week post-study drug visit. In addition, a summary of how many subjects developed a post-drug abnormal result will be presented.

Assessment of AEs reported after study drug discontinuation, i.e. during the post-study drug observation period, will be summarized separately by treatment group.

8.11 **Interim Analyses**

No interim analysis is planned.

8.12 Population Pharmacokinetics Analysis

The plasma concentrations of serlopitant and metabolites will be combined with the data from other serlopitant clinical studies for population PK analysis with PK endpoint of individual model parameter estimates and covariates identification. A specific population PK data analysis plan will be developed that will outline the detailed approach to data handling, model development and diagnostics, individual model parameter estimation, exploration of covariate effects, and final model evaluation techniques. The population PK analysis report will not be a part of the clinical study report.

9 ADMINISTRATIVE ASPECTS

9.1 Changes to the Protocol

Protocol amendments must be made only with the prior written approval of the Sponsor. An investigator signature will be obtained for the initial protocol and any amendments. Substantial amendments will be provided to the appropriate regulatory authorities. No protocol changes affecting the following will be made without the written approval of the Sponsor and the responsible IRB or EC:

- Safety and/or eligibility of subjects
- Data integrity
- Study design or conduct
- Willingness of a subject to participate in the study

9.2 Study Termination

The Sponsor has the right to terminate this study at any time. Reasons may include, but are not limited to, evidence of a potential safety risk in this study or other serlopitant studies or poor enrollment. The study may be terminated at the request of the US Food and Drug Administration, or if the approval to manufacture or to import study drug is revoked by those with jurisdiction. A written statement fully documenting the reasons for study termination will be provided to the IRB or EC.

9.3 Monitoring and Auditing Procedures

The Sponsor will designate study monitors who will be responsible for monitoring the conduct of this study. A separate study Monitoring Plan will include details regarding the responsibilities of the study monitors, investigator responsibilities in providing access to records and addressing issues identified, the frequency and structure of monitoring visits, and adherence to subject confidentiality as outlined in the Informed Consent Form (ICF).

9.4 Transfer of Obligations

The Sponsor will delegate certain aspects of study oversight to Contract Research Organizations (CROs). The specific responsibilities will be detailed in Transfer of Obligations documents.

9.5 Informed Consent

The purpose of the study, the procedures to be carried out, and any potential risks of study participation will be described in non-technical terms in the ICF. After having reviewed and understood the ICF, subjects will be required to read, sign, and date an IRB-approved or EC-approved consent form before any study-specific procedures are carried out. Subjects will be assured that they may withdraw from the study at any time without jeopardizing medical care related to or required as a result of study participation. The original signed consent form will be maintained in the investigator site file. Copies of signed consent forms will be provided to the subject.

9.6 Communication with the Institutional Review Board or Ethics Committee

The IRB or EC is constituted and operates in accordance with the principles and requirements described in the ICH E6 guideline. The protocol, ICF, other written subject information, and any proposed study advertising material must be submitted to the IRB or EC for written approval. IRB or EC approval of these documents will be provided to the investigator. The study will not start until the IRB or EC has granted its approval of the study materials and procedures.

Protocol amendments will be submitted to the IRB or EC as explained in [Section 9.1](#). SAE information will be submitted to the IRB or EC as explained in [Section 7.4](#).

If the study is terminated by the Sponsor, a written statement fully documenting the reason(s) for study termination will be provided to the IRB or EC.

9.7 Disclosure and Confidentiality

By signing this protocol, the investigator agrees to keep all information provided by the Sponsor in strict confidence and to require the same confidentiality from site staff and the IRB or EC. Study documents provided by the Sponsor (e.g. protocol, IB, eCRFs) will be stored appropriately to ensure their confidentiality. The information provided by the Sponsor to the investigator may not be disclosed to others without direct written authorization from the Sponsor, except to the extent necessary to obtain informed consent from subjects who wish to participate in the study.

The investigator must ensure that the subjects be identified by a unique subject study number. Other study-related documents that may contain confidential participant information (e.g. signed ICFs) will be kept in strict confidence by the investigator and be stored in a secure location with access restricted to the study staff.

9.8 Records and Electronic Case Report Forms

All study data except central laboratory, PK, eDiary, photography and ECG data will be recorded in an eCRF system. Data will be entered at the site by the appropriately designated and trained site personnel. All source documents from which eCRF entries are derived should be placed in the subject's medical records. eCRFs will be completed for every subject screened in the study.

The study monitor will review all eCRFs in detail and will have access to participant medical records, laboratory data, and other source documentation to allow required eCRF fields to be verified by source data.

Data consistency and plausibility checks against data entered into the eCRF will be included in the eCRF system. Data corrections can be performed in the eCRFs by the site. For each instance of data modification, the system requires a reason for change. The system keeps a full audit trail of the data values, the date and time of modification, and the electronic signature of the user who performed the change.

After a full review of the eCRFs by the study monitor and resolution of any data clarifications, the investigator will review, sign, and approve the subject's eCRF. All essential documents, source data, clinical records, and laboratory data will be retained by the site in accordance with the ICH E6 guideline and the site's data retention policies. These records must be available for inspection by the Sponsor, monitor, and regulatory authorities.

Further detail regarding data management and eCRFs is included in the Data Management Plan.

9.9 Good Clinical Practices and Ethical Study Conduct

The study procedures outlined in this protocol will be conducted in accordance with applicable ICH Guidelines, including ICH E6: Good Clinical Practices. As this study is conducted under a US IND, the investigator will also ensure that the basic principles of "Good Clinical Practice", as outlined in 21 CFR 312, subpart D, "Responsibilities of Sponsors and Investigators", 21 CFR, part 50 and 21 CFR, part 56 are adhered to.

The study procedures outlined in this protocol will also be conducted in accordance with the principles of the Declaration of Helsinki.

9.10 End of Study Notification

The Sponsor will notify appropriate regulatory authorities and the IRB or EC within 90 days from the end of the clinical study. The end of the clinical study is defined as the last study visit for the last subject.

9.11 Publication of Results

All publications (e.g. manuscripts, abstracts, oral/slide presentations, book chapters) based on this study or relying on data from this study must be submitted to the Sponsor for review and

release before submission for publication. The Sponsor is responsible for final approval of all publications.

9.12 Final Report

A clinical trial summary report will be provided to the appropriate regulatory authorities within one year of the end of the clinical study.

APPENDIX A SCHEDULE OF ACTIVITIES AND ASSESSMENTS

Table 2 Schedule of Visit Activities

Examination	Screening	Mid-Screening ^{TC}	Baseline ¹	Week 1 (± 3 days) ^{TC}	Week 2 (± 3 days)	Week 4 (± 3 days)	Week 6 (± 3 days)	Week 10 (± 7 days)	Post-drug obs.: 3 days (±1 day), and 7, 14, 21, & 28 days (±3 days) after Week 10 ²	Follow-up: 35 days (+3 days) after Week 10 ²	Early Treatment Discontinuation
Demographics	X										
Informed consent	X										
WI-NRS ³	X	X	X	X	X	X	X	X	X	X	X
DLQI			X			X		X			X
HADS, ESS			X			X		X	X	X	X
ECG	X				X	X		X		X	X
Vital signs	X		X		X	X	X	X	X	X	X
Medical history (and prior medications)	X	X	X								
Physical exam ⁴	X		X		X	X	X	X		X	X
Concomitant medications			X	X	X	X	X	X	X	X	X
Labs ⁵	X				X			X		X	X
Urine pregnancy test ⁶	X		X			X	X	X		X	X
PK blood draw					X	X		X			
Review of I/E criteria	X	X	X								
IGA PN-A and IGA PN-S			X		X	X		X		X	X
Photography (selected sites)			X					X		X	X
Dispense/review menstrual diary (if applicable)	X		X		X	X	X	X	X	X	X
Dispense/collect eDiary	X									X	X
eDiary review/compliance ⁷		X	X	X	X	X	X	X		X	
Dispense and/or collect study drug			X		X	X	X	X			X
Review study drug compliance					X	X	X	X			
AEs/SAEs ⁸	X	X	X	X	X	X	X	X	X	X	X

^{TC}Telephone Contact: The Mid-Screening telephone contact should only occur for subjects who require a washout longer than 2 weeks, at least 15 days prior to the scheduled Baseline visit.

¹All visits and windows should be scheduled based on the Baseline Visit (Day 1)

²The Post-Drug observation period visits occur 3 days (±1 day), and 7, 14, 21, and 28 days (±3 days), and the Follow-up visit occurs 35 days (+3 days) after the Week 10 visit or the last dose of study drug for subjects who discontinue study drug early.

³WI-NRS at Screening visit will be collected manually on paper for Inclusion/Exclusion criteria. All subsequent WI-NRS are collected daily via eDiary.

⁴Screening physical exam is complete and includes height and weight; other physical exams are targeted and include weight.

⁵Labs are ideally performed in the morning, particularly at visits with endocrine assessments (including Reproductive Endocrinology for females under 55 at age of consent) at Screening, Week 10 and Follow Up. Iron Studies, serum IgE and Serology labs are done only at Screening visit; endomysial antibody test and other optional studies only performed at Screening;

⁶Female subjects of childbearing potential only. Serum pregnancy test is required for positive or equivocal results

⁷See Table 3 for eDiary assessments

⁸During the period between informed consent and first study drug dose, only SAEs caused by a protocol-mandated intervention will be collected.

Table 3 Schedule of eDiary Assessments

An eDiary device is provided to subjects at the Screening visit and collected at the Follow-up visit.

Device	Assessment	Frequency and Duration of Assessment
eDiary	WI-NRS	Once daily from Screening/Mid-Screening visit through the Follow-up visit
eDiary	Dosing	Once daily from Baseline visit through Week 10 visit or study drug discontinuation

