5.6 Study Drug Discontinuation

Subjects should be discontinued from study drug treatment in the following situations:

- A female subject desires to become pregnant at the current time, stops contraception or expels her intrauterine device/implant, or becomes pregnant
- A female subject has new breast findings (e.g. a palpable mass or abnormal mammography, discharge), or has abnormal vaginal discharge or bleeding
- The subject decides to discontinue study drug treatment, or withdraws consent from the study
- The subject receives a strong CYP3A4 inhibitor (See [Appendix B](#))
- Any medical condition that may jeopardize the subject's safety if study drug is continued, in the investigator's and/or Sponsor's opinion; this may include the development of persistently (2 successive occasions) abnormal thyroid function tests (TSH >10, or TSH > 6 with low free T4; TSH <0.1, or TSH < 0.35 with high free T4); abnormal morning prolactin, cortisol, or corticotropin levels; or signs and symptoms of adrenal insufficiency

- Discontinuation is deemed to be in the best interest of the subject, in the investigator's and/or Sponsor's opinion, including evidence that the subject does not meet inclusion/exclusion criteria intended primarily for safety reasons, or a persistent lack of adherence to study procedures

The Sponsor or designee should be contacted within 24 hours of investigator's awareness of any study drug treatment discontinuation. Investigators should make every effort to contact the Sponsor or designee before discontinuing study drug treatment, if possible.

Subjects who discontinue treatment with study drug prior to completing the treatment period will enter a 5-week follow-up (post-study drug observation) period following the last dose of study drug (see [Section 3.1](#), [Section 6.5.10](#)). Every effort should be made for subjects to complete the 5-week observation period and the Follow-up visit after a subject has discontinued from study drug.

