6.1 Efficacy Parameters

6.1.1 *Itch Numeric Rating Scale*

The Itch NRS is a validated, self-reported instrument for measurement of itch intensity. It uses a 24-hour recall period and asks subjects to rate the intensity of their itch on an 11-point scale ranging from 0 (no itch) to 10 (worst itch imaginable). Higher scores indicate greater itch intensity. In this study, the subject is asked to rate the intensity of their *worst* itch (WI-NRS) during a 24-hour recall period; the questionnaire is provided in [Appendix C](#). Initial WI-NRS score collected during Screening visit will be collected on paper. All subsequent WI-NRS assessments will be reported by subject via eDiary. Subjects will record their WI-NRS scores once daily via eDiary at approximately the same time each day (+/- 3 hours) throughout the screening, treatment, and follow-up periods, as outlined in [Appendix A](#). Subjects may be allowed to adjust the timing of eDiary completion within the first week of Screening as needed. Standardized training and instructions will be provided to all subjects prior to eDiary use.

6.1.2 *Investigator's Global Assessment of PN Activity*

The IGA PN-A is an instrument used to assess the overall activity of PN lesions at a given time point, as determined by the investigator. It consists of a 5-point scale ranging from 0 (clear) to 4 (severe), as provided in [Appendix D](#). The IGA PN-A uses clinical characteristics of excoriations, crusting, and/or bleeding as guidelines for the overall activity assessment. The number of pruriginous lesions should not be considered for this assessment. IGA PN-A scores will be captured as outlined in [Appendix A](#). Each assessment during the study must be done by the Principal Investigator (PI) or designee. Every effort should be made to ensure that all assessments for a given subject are done by the same individual throughout the study. However, a change in assessor for a given subject, though not ideal, will not be considered a protocol deviation.

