- Perform targeted physical examination, including weight
- Assess and record any AEs and SAEs
- Collect returned study drug
- Utilize IWRS to assign new bottle of study drug
- Review eDiary for compliance, re-train subject as needed
- Confirm next scheduled visit

6.5.9 *Week 10 Visit*

The Week 10 visit occurs 70 days (\pm 7 days) after the Baseline visit. At the Week 10 visit, the following procedures and assessments are to be performed:

- Ask the subject to complete the DLQI, HADS, and ESS questionnaires
- Assess and record any changes in the subject's concomitant medications
- Female subjects should be queried for presence of new breast masses or abnormal discharge, and abnormal vaginal bleeding or discharge
- Review menstrual diary and record dates of menstrual flow (if applicable)

- Obtain ECG
- Obtain vital signs
- Perform targeted physical examination, including weight
- Perform IGA PN-A
- Perform IGA PN-S
- Perform a urine pregnancy test for females of childbearing potential (with positive or equivocal results confirmed by a serum pregnancy test)
- Draw blood for clinical laboratory tests (morning blood sampling due to Endocrine assessments)
 - Reproductive endocrine labs for females under 55 years of age at consent
 - Endocrine
 - Hematology
 - Chemistry
- Collect PK blood sample
- Assess and record any AEs and SAEs
- Collect returned study drug
- Obtain photos (at selected sites, only subjects that signed photography consent)
- Review eDiary for compliance, inform subject to continue entering WI-NRS score until Follow-up visit
- Review study drug compliance with re-training as required
- Confirm next scheduled visit date

6.5.10 ***Post-Drug Observation Visits***

There are five (5) post-drug observation visits, and a Follow-up visit to complete the post-observation period.

The Post-Drug Observation Visits occur 3 days (± 1 days), 7 days (± 3 days), 14 days (± 3 days), 21 days (± 3 days), and 28 days (± 3 days) after the Week 10 Visit.

At the Post-Drug Observation Visits, the following procedures and assessments are to be performed:

- Ask the subject to complete the HADS and ESS questionnaires
- Assess and record any changes in the subject's concomitant medications
- Female subjects should be queried for presence of new breast masses or abnormal discharge, and abnormal vaginal bleeding or discharge
- Review menstrual diary and record dates of menstrual flow (if applicable)
- Obtain vital signs
- Assess and record any AEs and SAEs

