6.5.11 *Follow-up Visit*

The required Follow-up visit (end of post-drug observation period) occurs 35 (+3 days) after the Week 10 visit or the last dose of study drug for subjects who discontinue study drug early.

At the Follow-up visit, the following procedures and assessments are to be performed:

- Register visit into the IWRS
- Ask the subject to complete the HADS and ESS questionnaires
- Assess and record any changes in the subject's concomitant medications
- Female subjects should be queried for presence of new breast masses or abnormal discharge, and abnormal vaginal bleeding or discharge
- Review menstrual diary and record dates of menstrual flow (if applicable)
- Obtain vital signs
- Perform targeted physical examination, including weight
- Perform IGA PN-A
- Perform IGA PN-S
- Obtain ECG
- Obtain photos (at selected sites, only subjects that signed photography consent)
- Perform a urine pregnancy test for females of childbearing potential (with positive or equivocal results confirmed by a serum pregnancy test)
- Draw blood for clinical laboratory tests (morning blood sampling due to Endocrine assessments)
 - Reproductive endocrine labs for females under 55 years of age at consent

- Endocrine
- Hematology
- Chemistry
- Assess and record any AEs and SAEs
- Collect eDiary device, review eDiary for compliance

6.5.12 *Early Termination*

Early termination of a subject from the study may occur due to loss to follow-up or withdrawal of consent by the subject. In accordance with legal requirements and International Conference on Harmonization (ICH) –GCP guidelines, every subject or his/her legal representative has the right to withdraw from the study at any time and without providing reasons. If provided, the reason (adverse event, study burden, lack of efficacy, other) a subject withdrew consent will be recorded in the electronic Case Report Form (eCRF). The PI or site staff must make every effort to contact subjects who are suspected of being lost to follow-up. Attempts to contact such subjects must be documented in the subject’s source documents.

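### Protocol Table 2 has the eDiary collected at early treatment discontinuation, while the rest of the protocol keeps daily WI-NRS entry through Follow-up; following the cell loses some observed primary and key secondary values

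*Protocol*

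**What the plan says.** Table 2 of Protocol Appendix A has a row "Dispense/collect eDiary" marked at Screening, Follow-up and Early Treatment Discontinuation. The device is issued at Screening, so the last mark can only mean collection.

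Other places say otherwise:

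- Table 3, same appendix: "An eDiary device is provided to subjects at the Screening visit and collected at the Follow-up visit". It schedules WI-NRS once daily through that visit.
- Section 6.1.1: WI-NRS is recorded daily "throughout the screening, treatment, and follow-up periods".
- Section 6.5.11: the Follow-up visit list includes "Collect eDiary device, review eDiary for compliance". The visit is timed "35 (+3 days) after the Week 10 visit or the last dose of study drug for subjects who discontinue study drug early".
- Table 2 itself: the WI-NRS row is marked at the post-drug and Follow-up visits, footnote 2 applies those visits to subjects who stop early, and footnote 3 says of WI-NRS after Screening: "All subsequent WI-NRS are collected daily via eDiary".
- Section 5.6 keeps early stoppers under observation for five weeks: "Every effort should be made for subjects to complete the 5-week observation period and the Follow-up visit".

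Section 6.5 has no procedure list for the early treatment discontinuation visit. Section 6.5.12 covers leaving the study and lists no visit procedures. The Week 10 list in 6.5.9 tells sites to "inform subject to continue entering WI-NRS score until Follow-up visit", but early stoppers have no equivalent instruction. Table 2 is therefore the only visit-level guidance for that visit.

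**The concern.** A subject whose device has been collected cannot make the daily entries that the other passages require. SAP 6.1.3 forms a weekly average only from four or more daily entries in the window, and mapping discontinuation-visit data to the nearest visit does not replace them. A missing weekly value is multiply imputed within arm (Protocol 8.2, SAP 6.1.5) unless a non-responder rule applies.

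Whether some stoppers' primary or key secondary value is observed or imputed would then depend on which table the site read. A serlopitant subject who stops for an adverse event and returns the device would be imputed from on-drug weeks alone and could be credited with an on-treatment response. The planned tipping-point analysis can probe that but cannot recover the data.

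**Working it through.** The plan states no figure for early discontinuation or for diary loss, so there is none to reproduce. The sample-size statement does not enter.

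**Inputs.** Windows (SAP 6.1.3): Week 2 = Days 8-14, Week 4 = Days 22-28, Week 10 = Days 64-70. Minimum entries: 4. Follow-up for early stoppers: last dose L + 35, up to L + 38 (Protocol 6.5.11 and Table 2, footnote 2). Off-drug entries are counted by study day, as the SAP windows read.

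**Cell followed.** The fourth day of week w is 7w - 3: Day 11 for Week 2, Day 25 for Week 4, Day 67 for Week 10. Return on Day 66 leaves at most three Week 10 entries (Days 64-66). Return on Day 67 leaves four if that day's entry is already made, otherwise three.

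**Device kept to Follow-up.** Entries possible on Days 64-70:

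| Last dose (Day) | Follow-up (Day) | Week 10 entries |
|---|---|---|
| 14 | 49-52 | 0 |
| 28 | 63-66 | 0-3 |
| 29 | 64-67 | 1-4 |
| 31 | 66-69 | 3-6 |
| 32 | 67-70 | 4-7 |
| 35 | 70-73 | 7 |

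Four entries need L + 35 ≥ 67, so L ≥ 32, or L + 38 ≥ 67, so L ≥ 29. The cell therefore costs the Week 10 average only for a last dose from about Day 29-32 with the discontinuation visit before Day 67. Of last-dose Days 1-66, it makes no difference to Week 10 on 28 days (42%) with the full +3 days, or on 31 days (47%) at nominal timing.

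**Weeks 2 and 4.** With the device kept, even a Day 1 stopper has entries to Day 1 + 35 = Day 36, so both weeks are complete. With the cell followed, return before Day 11 loses Week 2 and return before Day 25 loses Week 4.

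**Imputation.** The variable list (Protocol 8.2, SAP 6.1.5) is baseline and Weeks 1-10. Off-drug weekly scores would enter it if the device were kept. They are lost if the cell is followed, including for early stoppers whose Week 10 is missing either way.

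**Size.** Protocol 1.5.3 reports 3 serlopitant discontinuations for adverse events in the Phase 2 PN study. Arm sizes are inferred from the reported event rates: 46/64 = 71.9% and 39/63 = 61.9%. So 3/64 = 4.7% (exact 95% CI 1.0-13.1%). Assume stoppers are imputed at 40% but would respond at 22% off drug, near the midpoints of the 33-47% and 20-25% in Protocol 8.1.

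- Upper bound: 3/64 × (40 - 22) = 0.84 points (0.18-2.36 over the CI), or 140 × 0.0084 = 1.2 responders.
- Over the full quoted rates the gap is 33 - 25 = 8 to 47 - 20 = 27 points, giving 3/64 × 8 = 0.4 to 3/64 × 27 = 1.3 points.
- If last doses were spread evenly over Days 1-66 with the visit on the same day (assumptions), the share losing an observed Week 10 through the cell would be 35/66 to 38/66, giving about 0.45-0.49 of the 0.84 points. Earlier stoppers add something through the poorer imputation.

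**The case against.** Three counter-arguments carry weight.

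**The cell is outvoted.** Several passages say the device stays, and a careful site would notice. That makes the loss less likely but does not remove it, because no visit list corrects the cell.

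**Off-drug entries may not be meant to count as Week 10.** The SAP windows are by study day, which favours counting them. But post-treatment entries also have their own windows, and Protocol 8 limits LOCF to on-therapy observations. For a last dose on Day 49, Days 64-70 are post-treatment days 15-21, which is also the 3-Week Follow-up window. One entry can serve both summaries, and the follow-up table is descriptive, so the overlap is harmless; the missing explicit statement is not. If off-drug entries were excluded, the cell would not alter the observed Week 10 value. Calling the imputed rate overstated likewise presumes that off-drug itch is what Week 10 should measure, which no passage states.

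**Many stoppers are untouched.** Lack-of-efficacy cases and users of excluded therapy for worsening are non-responders by rule (Protocol 8.2, SAP 6.1.5 and 6.7). For subjects who leave the study, the withdrawal causes the loss.

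A reader might infer that every subject with a discontinuation visit before Day 67 loses Week 10 because of the cell. The table of last-dose days shows otherwise: for a last dose by Day 28 (Day 31 at nominal timing), the cause is a Follow-up visit tied to last dose.

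A reader might also take 0.9-2.7 points as the effect, from 5-15% stopping × 18 points. That is an upper bound over all stoppers, including those the cell cannot affect, and the documents give no support for the 5-15% range.

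**Conclusion.** The contradiction is real and should be corrected. Its reach is limited to subjects who stop drug, stay in the study, are not non-responders by rule, and attend a site that follows the cell. Among them, Week 10 is lost for a last dose from about Day 29-32 with the discontinuation visit before Day 67, Week 2 or Week 4 for device return before Day 11 or Day 25, and the off-drug scores that would inform imputation in every case.

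The likely effect on the serlopitant response rate is at most about 0.8 points, and less after unaffected subjects are removed. That rests on an inferred Phase 2 arm size, assumed rates of 40% and 22%, full reversion to the off-drug rate, and every site following the cell. It would rarely decide the trial. The reason to act is that observed-versus-imputed status should not depend on which table was read. The timing thresholds are firm, given study-day windows; the size is an assumption-based bound.

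**What to change.** 1. Footnote the Table 2 cell: collect the eDiary at Early Treatment Discontinuation only if the subject is also leaving the study; otherwise collect it at Follow-up, as in Table 3 and Section 6.5.11. Deleting the mark outright would be worse, because it is the only scheduled device retrieval for someone who leaves at that visit.
2. State in SAP 6.1.3 that off-drug entries on Days 64-70 count toward Week 10, subject to the existing non-responder rules.

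The footnote asks nothing that 6.1.1, 6.5.11 and Table 3 do not already require. Protocol 4.1 lets subjects stay on the version they consented to, so uptake may be mixed. The SAP line can be settled before unblinding even if collection has finished. The observed treatment difference may shrink slightly.

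Keeping the diary to Day 70 for the earliest stoppers would be new data collection. It is optional and should not delay these two changes.
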